11.2 Subject demographics and other baseline characteristics

All data for background and demographic variables will be listed by treatment group and subject. Summary statistics will be provided by treatment group.

Relevant medical history, current medical conditions, results of laboratory screens, drug tests and any other relevant information will be listed by treatment group and subject.

11.3 **Treatments**

Data for study drug administration and concomitant therapies will be listed by treatment group and subject.

Analysis of the primary variable(s) 11.4

11.4.1 Variable(s)

The primary efficacy variable is the articular cartilage bi-layer collagen organization evaluated with MRI at Week 16 and 28 (part A) and change from baseline in cartilage volume/thickness in the index region, assessed based on MRI at Weeks 28 and 52 (part B).

The primary safety variables are:

- Systemic and local Adverse Events
- **ECGs**
- Vital signs
- Hematology, blood chemistry, urinalysis

11.4.2 Statistical model, hypothesis, and method of analysis

The primary efficacy variables will be analyzed using the secondary PD analysis set and the primary safety variables using the safety analysis set.

11.4.2.1 Part A

The primary efficacy variable, articular cartilage bi-layer collagen organization, assessed based on MRI at Weeks cc116 and 28, will be analyzed using a mixed model repeated measures (MMRM) analysis of variance model, including baseline and all time points to compare treatment groups at Weeks CCI16 and Week 28. The model will include treatment, timepoint, treatment*timepoint, and type of lesion as fixed effects, subject as a random effect, and baseline measure as a fixed covariate. If deemed appropriate, the endpoint measure data will be transformed to facilitate analysis. 90% two-sided confidence intervals for the treatment effect will be formed at Weeks CCI16 and Week 28. Considering that the time course of response to LNA043 is not known, statistically significant differences between active drug and placebo at either Week 16 or Week 28 will be considered as a positive result.

11.4.2.2 Part B

The primary efficacy variable, change from baseline in cartilage volume/thickness in the index region, assessed based on MRI at Weeks 28 and 52. will be analyzed using a mixed model repeated measures (MMRM), including baseline and all time points to compare treatment groups at Week 28 and Week 52. The model will include baseline measure, treatment, timepoint, treatment*timepoint as fixed effects, participant as a random effect. 90% two-sided confidence intervals for the treatment effect will be formed at Weeks 28 and 52. If deemed appropriate, the endpoint measure data will be transformed to facilitate analysis. Considering that the time course of response to LNA043 is not known, statistically significant differences between active drug (either LNA043 dose) and placebo at either Week 28 or Week 52 will be considered as a positive result.

The safety variables will be summarized descriptively by treatment group for part A and part B.

Exploratory variables will be summarized descriptively by treatment group and associations with primary and secondary variables will be explored.

11.5 Handling of missing values/censoring/discontinuations

Commercially Confidential Information

Subjects with missing PK concentrations in some but not all periods will be included in a mixed model analysis assuming missing at random.

Missing data for MRI outcomes will not be imputed.

11.6 Summary statistics of safety

Vital signs

All vital signs data will be listed by treatment group, subject, and visit/time and if ranges are available abnormalities (and relevant orthostatic changes) will be flagged. Summary statistics will be provided by treatment and visit/time.

ECG evaluations

All ECG data will be listed by treatment group, subject and visit/time, abnormalities will be flagged. Summary statistics will be provided by treatment and visit/time.

Clinical laboratory evaluations

All laboratory data will be listed by treatment group, subject, and visit/time and if normal ranges are available abnormalities will be flagged. Summary statistics will be provided by treatment and visit/time

Adverse events

All information obtained on adverse events will be displayed by treatment group and subject.

The number and percentage of subjects with adverse events will be tabulated by body system and preferred term with a breakdown by treatment. A subject with multiple adverse events within a body system is only counted once towards the total of this body system.

The number (and proportion) of subjects with AEs of special Interest (AESI) will be summarized by treatment.

11.6.1 Sensitivity analyses

Not applicable.

11.7 Analysis of secondary variable(s)

Part A

The secondary efficacy variable, change in volume of cartilage defect filling, assessed based on MRI at Week 16 and 28, will be analyzed using a mixed model repeated measures (MMRM) analysis of variance model, including baseline and both timepoints to compare treatment groups at Week 16 and Week 28. The model will include treatment, timepoint, treatment*timepoint, and type of lesion as fixed effects, subject as a random effect, and baseline measure as a fixed covariate. 90% two-sided confidence intervals for the treatment effect will be formed at both Week 16 and Week 28. If deemed appropriate, the endpoint measure data will be transformed to facilitate analysis. Considering that the time course of response to LNA043 is not known, statistically significant differences between active drug and placebo at either Week 16 or Week 28 will be considered as a positive result.

Part B

The secondary efficacy variable, change from baseline in articular cartilage bi-layer collagen organization, assessed based on MRI at Weeks 28 and 52 will be analyzed using a mixed model repeated measures (MMRM). The model will include baseline measure, treatment, timepoint, treatment*timepoint as fixed effects, participant as a random effect. The model will be used to form 90% two-sided confidence intervals for the treatment effect at Weeks 28 and 52. If deemed appropriate, the endpoint measure data will be transformed to facilitate analysis. Considering that the time course of response to LNA043 is not known, statistically significant differences between active drug (either LNA043 dose) and placebo at either Week 28 or Week 52 will be considered as a positive result.

11.7.1 Efficacy / Pharmacodynamics

Not Applicable.

11.7.2 Pharmacokinetics

LNA043 serum and synovial fluid concentration data will be listed by subject, and visit/sampling time point. Descriptive summary statistics will be provided by treatment and visit/sampling time point, Commercially Confidential Information

Summary statistics will include mean (arithmetic and geometric), Standard Deviation (SD), CV (arithmetic and geometric), median, minimum and maximum. An exception to this is Tmax where median, minimum and maximum will be presented.

Commercially Confidential Information . A geometric mean will not be reported if the dataset includes zero values. Pharmacokinetic parameters will be calculated as described in Section 8.7 and will be listed by treatment and subject.

11.7.3 Pharmacokinetic / pharmacodynamic interactions

Not Applicable.

11.7.4 Immunogenicity

All immunogenicity results will be listed by treatment group, subject and visit/time.

11.7.5 Other assessments

Not Applicable

11.8 Analysis of exploratory variables

Commercially Confidential Information

11.9 Sample size calculation

11.9.1 Part A

Commercially Confidential Information

A sample size of 36 LNA043 treated patients and 12 Placebo patients (48 patients, 3:1 LNA043:Placebo) will allow for approximately 90% power, with a 1-sided alpha of 0.05, to detect a 20% relative difference between LNA043 and Placebo overall, and CCI . Stated differently, a two-sided 90% confidence interval for the treatment effect will exclude zero with probability 90%.

A 20% relative improvement in T2 mapping between treatments is considered to be potentially clinically meaningful and statistically different than the 10% random variability. So, in the calculations above, an effect size of 0.2/0.18=1.11 is used.

Page 95 Protocol No. CLNA043X2202

Commercially Confidential Information

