In Part A, the study population will be comprised of male and female patients with partial thickness cartilage lesions of one knee. A total of approximately 60 patients will be enrolled in the study and randomized. Randomization will be stratified by type of lesion (femoral condyle or patella). At least 48 patients are expected to complete the study (20% drop out rate). Additional patients may be enrolled if the dropout rate will exceed 20%.

The investigator must ensure that all patients included in the study meet the eligibility criteria. No additional criteria should be applied by the investigator, in order that the study population will be representative of all eligible patients. Patient selection is to be established by checking through all eligibility criteria at screening and before dosing. A relevant record (e.g. checklist) of the eligibility criteria must be stored with the source documentation at the study site.

Deviation from any entry criterion excludes a patient from enrollment into the study.

Commercially Confidential Information

Part B

In Part B, the study population will be comprised of male and female patients with knee OA (K&L 2-3). A total of approximately 75 patients will be enrolled in the study and randomized. At least 69 patients are expected to complete the study (10% drop out rate). Additional patients may be enrolled if the dropout rate will exceed 10%. The investigator must ensure that all patients included in the study meet the eligibility criteria. No additional criteria should be applied by the investigator, in order that the study population will be representative of all eligible patients. Patient selection is to be established by checking through all eligibility criteria at screening and before dosing. A relevant record (e.g. checklist) of the eligibility criteria must be stored with the source documentation at the study site.

In total, 135 patients are expected to be randomized into the study.

Deviation from any entry criterion excludes a patient from enrollment into the study.

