6.1.3 Statistical model, assumptions and hypotheses

6.1.3.1 Part A

The primary efficacy variable for Part A, change from baseline in articular cartilage bi-layer collagen organization will be analyzed using a mixed effect model for repeated measures (MMRM) analysis of variance model for each layer (deep and superficial) separately and for both layers combined, and region; including all-time points to compare treatment groups at Weeks 16 and 28. The model will include baseline as a covariate, treatment, timepoint, treatment*timepoint and type of lesion as fixed effects and subject as a random effect.

A two-sided 90% confidence intervals for the treatment effect will be formed at Weeks 8, 16 and 28. Considering that the time course of response to LNA043 is not known, statistically significant differences (one-sided p-value of treatment superiority to placebo at 95% significance level) between active drug and placebo at either Week 16 or Week 28 will be considered as a positive result.

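### Part A sample size (Protocol 11.9.1): the printed inputs give about 95% power, not about 90%

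*Protocol*

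**What the plan says.** Protocol 11.9.1 sets out the Part A calculation. "A sample size of 36 LNA043 treated patients and 12 Placebo patients (48 patients, 3:1 LNA043:Placebo") is said to be a size that "will allow for approximately 90% power, with a 1-sided alpha of 0.05, to detect a 20% relative difference between LNA043 and Placebo overall". The same claim is then put in interval form: "a two-sided 90% confidence interval for the treatment effect will exclude zero with probability 90"%. The section closes by saying that, for the calculations just described, "an effect size of 0.2/0.18=1.11 is used".

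Three other places bear on the inputs:

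- Protocol section 4 (Population, Part A) plans about 60 randomized patients and adds: "At least 48 patients are expected to complete the study (20% drop out rate").
- Protocol 11.4.2.1 describes the analysis as a repeated-measures model with "type of lesion as fixed effects, subject as a random effect, and baseline measure as a fixed covariate", and says that "90% two-sided confidence intervals for the treatment effect will be formed".
- SAP 6.1.3.1 defines significance by a "one-sided p-value of treatment superiority to placebo at 95% significance level", which I read as a one-sided 5% test.

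The level in the sample-size section therefore matches the level at which the data are to be analysed.

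**The concern.** Group sizes, alpha and standardized effect together fix the power of a two-sample comparison. All of them are printed, and the power they give is not the power that is stated. As written, the planned chance of missing a true 20% difference is about 10%; the printed inputs make it about 5%.

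What is at stake is whether the planning basis can be reproduced. The target effect is clear. A mismatch of this size suggests either that the power figure is wrong or that one printed input, possibly the alpha, is not the one used. If it is the alpha, the interval sentence is also tied to the wrong confidence level.

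**Working it through.** **Inputs**

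- n1 = 36, n2 = 12, one-sided alpha = 0.05 (Protocol 11.9.1).
- Difference 0.2, denominator 0.18, so d = 0.2/0.18 = 1.111 (Protocol 11.9.1).
- 48 is net of dropout: 60 × (1 − 0.20) = 48 (Protocol section 4).

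**Power at the stated inputs**

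- Standard-error factor: sqrt(1/36 + 1/12) = sqrt(4/36) = 0.333.
- Noncentrality: 1.111/0.333 = 3.33.
- Normal approximation: Φ(3.333 − 1.645) = Φ(1.688) = 0.954.
- Noncentral t with 36 + 12 − 2 = 46 degrees of freedom: 0.949.

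The stated 90% is not reproduced; the gap is about 5 percentage points. A two-sided 90% interval excludes zero in the favourable direction exactly when the one-sided 5% test rejects, so the interval sentence carries the same 94.9%.

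**Does an ordinary choice of method explain it?** (d = 1.11, one-sided 0.05)

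| Variant | Power |
|---|---|
| One degree of freedom for lesion type (df 45) | 94.9% |
| Welch t (simulated) | 94.0% |
| Rank-sum, normal data (simulated) | 93.5% |
| Rank-sum at its lower efficiency bound of 0.864 | 91.9% |
| t with deliberately conservative df 11 | 92.9% |
| Baseline-adjusted, assumed baseline correlation 0.3 / 0.5 | 96.4% / 98.4% |
| All randomized patients, 45:15 | 97.9% |
| A second 20% dropout, 29:10 | 90.8% |

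The two baseline correlations are assumptions; the documents give none. They show only the direction: if 0.18 is an unadjusted standard deviation, the planned covariate raises power and widens the gap. The 29:10 row comes close to 90% only by counting dropout twice.

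**Which single changes bring back 90%?** (36:12, noncentral t)

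| Change | Power |
|---|---|
| One-sided alpha 0.025 | 90.4% (normal 91.5%) |
| Denominator 0.20, so d = 0.2/0.20 = 1.00 | 90.5% |
| Log-scale effect, d = ln(1.2)/0.18 = 1.013 | 91.1% |

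Each of these contradicts something printed in 11.9.1. Solving for exactly 90% at 36:12 and one-sided 0.05 gives d = 0.99, which is a denominator of 0.2/0.99 = 0.202 rather than 0.18.

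**The case against.** The strongest reply is that the power sentence is incomplete in the public text. There is a redacted block before it, a redacted clause within it and more redacted text after it. The test, the model or a joint or subgroup condition could be there, and redacted text does not count as missing from the plan. A joint condition can even give the stated figure with every printed input unchanged: the Part A endpoint covers superficial and deep layers, SAP 6.1.3.1 models each layer separately, and two independent comparisons at 94.9% both succeed with probability 0.949 × 0.949 = 0.901. It can also be said that the figure is only claimed as approximate, that the planned analysis is a repeated-measures model rather than a t-test, and that nothing practical follows.

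Part of this stands. The redaction means that the cause cannot be named from the documents, and the remedy has to leave room for a further assumption. The consequence is documentary only, and the interval sentence is the same discrepancy in other words, not a second one.

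The joint-success route does not fit the visible text. The protocol ties 1.11 directly to the calculation and restates the 90% as the chance that one interval, for the treatment effect, excludes zero. The visible success rule is also significance at either Week 16 or Week 28, which can only raise the chance of success above the single-visit figure. Approximation does not cover the gap either, since it halves the stated miss probability. Nor does the choice of model, because useful baseline adjustment moves power upward.

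**Conclusion.** The concern holds, as a minor one. On the visible inputs and a simple two-sample comparison, power is 94.9% (t) or 95.4% (normal) against a stated figure of about 90%, and the interval-exclusion probability is wrong by the same amount.

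This rests on reading 0.18 as the between-patient standard deviation on the scale of the 0.2 difference, which is how the protocol uses it, and on 48 being evaluable completers. The arithmetic is firm. The cause is not known: one-sided 0.025, a denominator near 0.20, a log scale and an undisclosed assumption all remain possible.

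The discrepancy runs in the safe direction. On these inputs Part A has more power than claimed, in a study described as non-confirmatory, and no sample size, analysis or decision depends on the correction.

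**What to change.** The sponsor should reconcile power, alpha and effect size in Protocol 11.9.1.

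- **If the sample size, alpha and effect size stand as printed:** restate both the power and the probability that the 90% interval excludes zero as about 95%. This keeps the section in line with Protocol 11.4.2.1 and SAP 6.1.3.1.
- **If one input differs from what was used, or a further assumption applied:** correct that input or state the assumption, and make the interval sentence match. For example, had the calculation used one-sided 0.025, the sentence would have to refer to a 95% interval, and the protocol should then acknowledge the difference from the 90% interval in 11.4.2.1.

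The cost is two corrected sentences. Sample size, model, threshold and success rule are unchanged.

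### Part A's printed one-sided alpha of 0.05 and 90% power describe a single test; the either-week success rule has a false-positive rate above 5%, and the 90% does not follow from the printed inputs

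*Protocol*

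**What the plan says.** **Sizing (protocol 11.9.1).** The basis is "A sample size of 36 LNA043 treated patients and 12 Placebo patients (48 patients, 3:1 LNA043:Placebo"). This is said to give "approximately 90% power, with a 1-sided alpha of 0.05, to detect a 20% relative difference between LNA043 and Placebo overall". The claim is then put in terms of one interval: "Stated differently, a two-sided 90% confidence interval for the treatment effect will exclude zero with probability 90" percent. On the inputs, the section says that "an effect size of 0.2/0.18=1.11 is used". The rest of the section is partly redacted.

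**Success rule (protocol 11.4.2.1).** Because the timing of any response is unknown, "statistically significant differences between active drug and placebo at either Week 16 or Week 28 will be considered as a positive result". SAP 6.1.3.1 repeats this: a significant difference "between active drug and placebo at either Week 16 or Week 28 will be considered as a positive result". It adds that the test is one-sided for superiority, at a level it words as 95%. I read this as one-sided 0.05 at each week, which matches the 90% two-sided intervals planned at those visits.

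**Adjustment.** The readable Part A text neither adjusts for the two weeks nor states an overall error rate. The SAP does say that it will not adjust for multiplicity, but only in 6.1.3.2, for Part B.

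**Which measure.** SAP 6.1.3.1 fits the model to the deep layer, the superficial layer, both combined, and by region. It does not say which of these the success rule applies to.

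**The concern.** The alpha and power in 11.9.1 belong to one comparison, whereas the rule that declares Part A positive gives the drug two chances, each at the full level. The false-positive rate of that rule must exceed 5% unless the two weeks' results are perfectly correlated.

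This matters because Part A is the proof-of-concept part, and protocol 3.2.2 cites its positive results among the grounds for Part B. A reader who takes 5% as the risk of calling an inactive drug positive is using too low a figure. The sizing paragraph has a second problem: its stated power cannot be recovered from its stated inputs, so it is unclear which level or effect size the 48 patients were chosen for.

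**Working it through.** **Inputs from the documents:** 36 vs 12 patients, effect size 0.2/0.18 = 1.111, one-sided alpha 0.05 and stated power of about 90% (protocol 11.9.1); success at Week 16 or Week 28 (protocol 11.4.2.1, SAP 6.1.3.1); 60 randomized and 20% dropout (protocol section 4).

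**Assumed input:** the correlation rho between the Week 16 and Week 28 treatment estimates. It is not given, so I use 0 to 0.95. It should be positive, since both estimates come from the same patients.

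**Step 1: the plan's own figures.** The dropout allowance reproduces: 48/0.8 = 60.

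The power does not. The noncentrality is 1.111 × sqrt(36 × 12/48) = 1.111 × 3 = 3.333. Normal power at one-sided 0.05 is Φ(3.333 − 1.645) = Φ(1.688) = 95.4%; the noncentral t with 46 degrees of freedom gives 94.9%. Nearby settings compare as follows.

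| Effect size | One-sided level | Power, normal | Power, t |
|---|---|---|---|
| 1.11 (printed) | 0.05 (printed) | 95.4% | 94.9% |
| 1.11 | 0.025 | 91.5% | 90.4% |
| 1.0 | 0.05 | 91.2% | 90.5% |
| 1.0 | 0.025 | 85.1% | 83.6% |

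The printed 90% therefore fits either one-sided 0.025 with the printed effect size, or an effect size of about 1.0 at 0.05. The readable text does not say which.

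**Step 2: false-positive rate of the either-week rule, one T2 measure.** With no effect at either week, the rate is 1 − P(Z16 ≤ 1.645 and Z28 ≤ 1.645), bivariate normal with correlation rho. At rho = 0 this is 1 − 0.95² = 9.75%.

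| rho | 0 | 0.3 | 0.5 | 0.7 | 0.8 | 0.9 | 0.95 |
|---|---|---|---|---|---|---|---|
| Rate | 9.75% | 9.3% | 8.8% | 8.0% | 7.5% | 6.8% | 6.3% |

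Simulated pooled t-tests with 36 vs 12 (200,000 trials per value) gave 9.7%, 8.7%, 8.0%, 7.5% and 6.8% at rho 0, 0.5, 0.7, 0.8 and 0.9. Against the printed 5%, the range is a factor of 6.3/5 = 1.26 to 9.75/5 = 1.95.

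**Step 3: power of the either-week rule.** If the effect of 1.11 is present at both weeks, simulated power is 99.7%, 98.8%, 97.4% and 96.7% at rho 0, 0.5, 0.8 and 0.9. The rule raises power.

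**Step 4: one-sided 0.025 per week, for comparison.** The either-week false-positive rate is 4.94% at rho 0, 4.54% at 0.5, 3.90% at 0.8 and 3.52% at 0.9, so it stays below 5%. Single-week power is 90.4% at effect size 1.11, down from 94.9%.

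**The case against.** The strongest case for leaving the plan alone is that the study is labelled non-confirmatory. The either-week rule and its reason are stated openly, and the SAP declines adjustment for the parallel Part B rule. The interval sentence in 11.9.1 is also a correct restatement for one test and claims no overall error rate. Unadjusted testing at each visit is a defensible choice for proof of concept. All of that stands, and it keeps the remedy modest. It does not make 5% the error rate of the written rule, and an unknown time course justifies two looks without making their combined risk 5%.

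Redacted text in 11.9.1, or in SAP sections 2, 3 and 6.1.4, might give the rule's operating characteristics. That cannot be excluded. The two Part A decision rules are legible on this point, though, and contain no adjustment.

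A reader might infer three stronger things that the documents do not support:

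- **That moving to 0.025 per week costs nothing**, because the printed 90% is still met. This relies on the unexplained gap between 90% and 94.9%. If the calculation really used an effect size near 1.0, power at 0.025 would be about 84%.
- **That the sponsor already meant 0.025 per week**, because it reproduces the 90%. The interval sentence and the SAP both point to 0.05 per test.
- **That the threshold can simply be tightened now.** Protocol 3.2.2 already cites positive Part A results, and protocol 1.3.1 tabulates adverse events by arm. Changing the success criterion after efficacy results are known would be a problem of its own.

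**Conclusion.** The point holds as a mismatch between the printed operating characteristics and the rule to be applied. For one T2 measure, the either-week rule has a one-sided false-positive rate of about 6.3% to 9.75% for a between-week correlation from 0.95 down to 0. That range is conditional: the correlation is assumed, and the upper end needs independence between two visits on the same patients, which is unlikely. A fixed figure such as 7% to 10% would be too definite, since the rate falls below 7% once the correlation exceeds about 0.88. In the other direction, the range is too low if any of several layers or regions may count, and SAP 6.1.3.1 leaves that open.

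The printed inputs give about 95% single-week power at one-sided 0.05, not about 90%. This is an unreconciled figure and not a power shortfall. Nor does any of this show that the Part A result behind Part B was a false positive; it shows only that its stated risk was too low.

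**What to change.** **Protocol 11.9.1:** restate 0.05 as the one-sided rate per week. Give the either-week false-positive rate with the correlation assumed for it. Reconcile the 90% with 36 vs 12 and effect size 1.11, by correcting the power, the level or the effect size, whichever was actually used.

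**SAP 6.1.3.1:** name the one T2 measure (layer and region) to which the success rule applies, and report a positive Part A result together with the overall error rate. Without that designation, no single overall rate can be stated correctly. If Part A results are already known, the report should say that the measure was designated afterwards.

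These are wording changes and need no patients, visits or data.

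**Option, only if Part A results have not yet been seen:** require one-sided 0.025 at Week 16 or at Week 28 and keep the 90% intervals for estimation. This caps the rate at 5%. The price is single-week power of about 90% instead of about 95% at effect size 1.11, and less if the true planning effect was smaller.
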